6.3.5.6 Monitoring guideline for hyperglycemia suspected to be related to dabrafenib treatment

Hyperglycemia requiring an increase in the dose of, or initiation of insulin or oral therapy can occur with dabrafenib. Monitor serum glucose levels as clinically appropriate during treatment with dabrafenib in subjects with pre-existing diabetes or hyperglycemia.

Advise subjects to report symptoms of severe hyperglycemia such as excessive thirst or any increase in the volume or frequency of urination.

6.3.5.7 Mandatory dose modification and management guideline for hemorrhage

Hemorrhage, including major hemorrhage defined as symptomatic bleeding in a critical area or organ, can occur when dabrafenib is administered with trametinib. Permanently discontinue dabrafenib and trametinib for all Grade 4 hemorrhagic events and for any persistent Grade 3 hemorrhagic events. Withhold dabrafenib and trametinib for Grade 3 hemorrhagic events; if improved, resume at the next lower dose level.

6.3.5.8 Mandatory dose modification and management guideline thromboembolic events

Advise patients to immediately seek medical care if they develop symptoms of deep vein thrombosis (DVT) or pulmonary embolism (PE), such as shortness of breath, chest pain, or arm or leg swelling. If any signs or symptoms of venous thromboembolism are present, the subject will undergo specific laboratory and medical imaging studies to confirm it. The medical imaging study or studies selected will depend on the anatomic site or organ of involvement (e.g., Doppler ultrasound, venography, ventilation perfusion lung scan, angiography, MRI). If the diagnosis is confirmed, appropriate medical care according to standard local clinical practice should be initiated immediately.

Permanently discontinue trametinib for life threatening PE. Withhold trametinib for uncomplicated venous thromboembolism for up to 3 weeks; if improved, trametinib may be resumed at a lower dose level.

6.3.5.9 Guideline dose modification and management for hemophagocytic lymphohistiocytosis (HLH)

In post marketing experience, hemophagocytic lymphohistiocytosis (HLH), has been observed with dabrafenib and trametinib combination therapy. Since post-marketing adverse drug reactions are reported from a population of uncertain size, the exact frequency of HLH in patients receiving dabrafenib and trametinib is unknown. HLH is a rare, life-threatening condition caused by an overactive, abnormal response of the immune system ([Kikuchi et al 2022](#)). HLH is associated with a constellation of multiple clinical and laboratory features that may include fever, hepatosplenomegaly, hypertriglyceridemia, hypofibrinogenemia, high serum ferritin, multilineage cytopenias and hemophagocytosis. If HLH is suspected, treatment should be interrupted. If HLH is confirmed, treatment should be permanently discontinued and appropriate management of HLH per institutional standards should be initiated.

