Period	A subdivision of the study timeline; divides stages into smaller functional segments such as screening, baseline, titration, washout, etc.
Personal data	Subject information collected by the Investigator that is transferred to Novartis for the purpose of the clinical trial. This data includes patient identifier information, study information and biological samples.
Randomization number	A unique treatment identification code assigned to each randomized patient, corresponding to a specific treatment arm assignment
Stage related to study timeline	A major subdivision of the study timeline; begins and ends with major study milestones such as enrollment, randomization, completion of treatment, etc.
Stage in cancer	The extent of a cancer in the body. Staging is usually based on the size of the tumor, whether lymph nodes contain cancer, and whether the cancer has spread from the original site to other parts of the body
Stop study participation	Point/time at which the patient came in for a final evaluation visit or when study treatment was discontinued whichever is later
Study treatment	Includes any drug or combination of drugs in any study arm administered to the patient (subject) as part of the required study procedures, including placebo and active drug run-ins. In specific examples, it is important to judge investigational treatment component relationship relative to a study treatment combination; study treatment in this case refers to the investigational and non-investigational treatments in combination.
Study treatment interruption	Includes any delay or withholding of study treatment for any reason as well as an interruption during an infusion of study treatment for any reason
Study treatment discontinuation	Point/time when patient permanently stops taking study treatment for any reason
Treatment group	A treatment group defines the dose and regimen or the combination, and may consist of 1 or more cohorts. Cohorts are not expanded, new cohorts are enrolled.

Variable	Identifier used in the data analysis; derived directly or indirectly from data collected using specified assessments at specified time points
Withdrawal of study consent	Withdrawal of consent from the study occurs only when a subject does not want to participate in the study any longer, and does not allow any further collection of personal data

Amendment 7 (27-Jan-2023)

Amendment rationale

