6.1 Study treatment

For this study, the investigational drug is PDR001, and the study treatment is PDR001 or placebo in combination with dabrafenib 150 mg BID and trametinib 2 mg QD.

PDR001 will be supplied in vial in liquid or powder for solution for infusion pharmaceutical form. PDR001 (liquid or reconstituted powder) will be diluted in dextrose 5% in water (D5W). Due to incompatibility, 0.9% sodium chloride solution must not be used.

Placebo will be a D5W for infusion supplied by the site.

Infusion must take place in a facility with appropriate resuscitation equipment available at the bedside and a physician readily available during the period of drug administration.

Trametinib will be provided as 0.5 mg and 2 mg tablets, and dabrafenib as 50 mg and 75 mg capsules for oral administration.

All dosages prescribed and dispensed to subjects and all dose changes during the study must be recorded on the Dosage Administration Record (DAR) eCRF.

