6.3 Dose modifications and reductions

Adverse events of special interest (AESI) include AEs of a potential irAE that are associated with PDR001 treatment. An irAE may be experienced by subjects treated with PDR001 due to its mechanism of action and predicted based on the reported experience with other immunotherapies that have a similar mechanism of action. Investigators must be vigilant and carefully identify AEs that may be suggestive of potential irAEs as their appearance may be sub-clinical and early diagnosis is critical for its adequate management and resolution.

An irAE is typically low grade and self-limited, often occurring after multiple doses, and most frequently involving the GI tract (diarrhea/colitis), skin (rashes), liver (hepatitis), lung (pneumonitis), kidneys (nephritis) and endocrine systems (a variety of endocrinopathies) and rarely CNS (encephalitis). Serological, immunological and histological assessments should be performed as deemed appropriate by the investigator, to verify the potential immune-related nature of the AE, and exclude a neoplastic, infectious or metabolic origin of the AE.

Severe grade or persistent lower grade irAEs typically require interrupting or permanently discontinuing treatment and administration of systemic steroids or other non-corticosteroid immunosuppressive medication when systemic steroids are not effective. Early recognition of irAEs and initiation of treatment are critical to reduce the risk of complications, since the majority of irAEs are reversible with the use of steroids and other immune suppressants.

In some cases, it may be unclear to determine if an adverse event is immune related or not, thus the following dose reduction guidelines should be followed.

The following sections address the specific instructions for mandatory dose modifications and recommended management for AEs considered suspected to be related to study treatment. For subjects who do not tolerate the protocol-specified dosing schedule, dose interruptions or modifications are mandated in order to allow subjects to continue study treatment.

No dose reductions are allowed for PDR001. Dose interruption for PDR001/placebo includes delaying or withholding the treatment for any reason as well as an interruption of treatment during an infusion. All dose interruptions and the reason for the dose interruption must be

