General		X	X	Section 6.3.5 Table 6-21

Adverse Events	PDR001	dabrafenib	trametinib	Guideline
LVEF		X	X	Section 6.3.5.1 Table 6-22
Hypertension		X	X	Section 6.3.5.2 Table 6-23
New malignancies		X	X	Section 6.3.5.3.
Pyrexia syndrome		X	X	Section 6.3.5.4 Table 6-24
Visual changes		X (Uveitis)	X (RVO)	Section 6.3.5.5 Table 6-25
RPED			X	Section 6.3.5.5 Table 6-26
Hyperglycemia		X		Section 6.3.5.6
Hemorrhage		X	X	Section 6.3.5.7
Thromboembolic events			X	Section 6.3.5.8
Hemophagocytic lymphohistiocytosis		X	X	Section 6.3.5.9
"X" indicates study treatment (s) that may need to be modified.				

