6.3.4.1 Guidance for corticosteroids tapering for management of immune-related AEs

Reduce prednisone dose by 2.5 to 5.0 mg decrements every 3–7 days until physiologic dose (5 to 7.5 mg of prednisone per day) is reached. Consider to complete tapering over a period of at least 4 weeks. Slower tapering of corticosteroids therapy may be recommended if the adverse event is not showing improvement. Once corticosteroid tapering is achieved at a level of ≤ 10 mg of prednisone/day (or equivalent), PDR001 can be restarted as indicated in the dose modification tables.

6.3.5 Dose modification and management guideline for adverse events suspected to be related to dabrafenib and/or trametinib

Continue PRD001/placebo.

For adverse events of special interest reported **only for dabrafenib and/or trametinib**, general guidelines for dose modification in [Table 6-21](#) should be followed for dabrafenib and trametinib.

In general, if an AE resolves to Grade 1 or baseline at the reduced dose level, and no additional toxicities are seen after 4 weeks of study treatment at the reduced dose, the dose may be increased to the previous dose level.

A dose reduction below 50 mg BID for dabrafenib or below 1 mg QD for trametinib is not allowed. If a dose reduction below 50 mg BID for dabrafenib is required, dabrafenib will be permanently discontinued but these subjects will be allowed to continue trametinib. If a dose reduction below 1.0 mg QD for trametinib is required, then trametinib will be permanently discontinued, but these subjects will be allowed to continue dabrafenib.

[figure not shown]

Table 6-21 General guidelines for dose modification for adverse events suspected to be related to dabrafenib and/or trametinib treatment

Grade	Recommended adverse event management guidelines	Mandatory dose modification requirements
Grade 1 or Grade 2 tolerable	
 Monitor closely. Provide supportive care according to institutional standards. 	
 Continue dabrafenib and trametinib at the same dose level.

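### The HLH rule names no drug and, read where it stands in Section 6.3.5, most naturally keeps PDR001 going through a life-threatening immune event

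*Protocol*

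**What the plan says.** Section 6.3.5.9 was added by Amendment 7, which lists updated HLH safety information among its main purposes. It reports HLH from post-marketing use of dabrafenib with trametinib, says the frequency is unknown, and describes HLH as rare, life-threatening and caused by an overactive immune response. It then gives two instructions. On suspicion, treatment is interrupted. On confirmation: "If HLH is confirmed, treatment should be permanently discontinued and appropriate management of HLH per institutional standards should be initiated". No drug is named in either.

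The section belongs to 6.3.5, whose title limits it to "adverse events suspected to be related to dabrafenib and/or trametinib" and whose first line is "Continue PRD001/placebo". Table 6-8 in Section 6.3 marks dabrafenib and trametinib for HLH and leaves the PDR001 cell empty. Its footnote explains that an X "indicates study treatment (s) that may need to be modified".

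Elsewhere, Section 6.1 states that "the study treatment is PDR001 or placebo in combination with dabrafenib 150 mg BID and trametinib 2 mg QD". The glossary says of a combination that "study treatment in this case refers to the investigational and non-investigational treatments in combination".

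**The concern.** Sites need to know from this rule which of three drugs to stop. The local text steers them to stop two and keep the third, an antibody that works by releasing an immune checkpoint, during an event that the same paragraph attributes to immune overactivation and calls life-threatening. No reason is given for keeping PDR001, and nothing in 6.3.5.9 says PDR001 is not implicated. For a patient taking all three drugs, a site may be unable to tell which one is responsible.

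What is at stake is patient safety. Sample size, power, type I error and the PFS and OS analyses do not depend on it.

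**Working it through.** There is no figure to reproduce, so the check sets the texts side by side.

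1. **What the local text implies for PDR001.** Three things agree. The 6.3.5 lead-in continues PDR001 or placebo. The HLH row of Table 6-8 does not list PDR001 among the drugs that may need modification. The word used is a local one: Table 6-26 speaks of continuing treatment where the event is suspected to be related to trametinib, and both the opening of 6.3.5 and Table 6-23 speak of study treatment at a reduced dose. Sections 6.3 and 6.3.1 allow no dose reduction of PDR001, so in those two places even the longer term can only mean dabrafenib and trametinib.

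2. **What neighbouring rules do.** Section 6.3.5.7 (hemorrhage) names dabrafenib and trametinib. Section 6.3.5.8 (thromboembolism) names trametinib. Section 6.3.3.4 names all three drugs for Stevens-Johnson syndrome and toxic epidermal necrolysis. The HLH rule leaves the reader to infer them.

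3. **What the general rules would do.** Table 6-18 covers related non-hematologic and laboratory events other than neutropenia and thrombocytopenia. At a first Grade 4 event it interrupts all three drugs and permanently discontinues PDR001 or placebo, unless a benefit-risk assessment supports restarting. Its default is therefore the reverse of the one in 6.3.5. Because HLH can present with cytopenias, a site could dispute whether it falls in this table's scope, and the protocol does not say.

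4. **What happens if PDR001 is suspected.** Section 6.3.1 requires permanent discontinuation of PDR001 only if the event has not recovered to Grade 1 or baseline within 12 weeks, or if steroids stay above 10 mg/day for more than 12 weeks. HLH that resolves sooner would not trigger a permanent stop of PDR001 by that route, whereas confirmed HLH permanently stops the other two drugs at once.

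5. **What happens if the cause is unclear.** Section 6.3 says that "it may be unclear to determine if an adverse event is immune related or not, thus the following dose reduction guidelines should be followed", which sends the site back to the same guidelines. It refers sites to the PDR001 Investigator's Brochure for issues the protocol does not mention, and HLH is mentioned.

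6. **How many patients.** The Amendment 7 rationale gives 2 patients on treatment in Part 1, 1 in Part 2 and 88 in Part 3: 2 + 1 + 88 = 91. The number on PDR001 is not stated. It is lower than 91 unless every one of the 88 was in the PDR001 arm, because placebo had stopped by then (Section 6.5.3). Expected HLH cases cannot be calculated without a rate, and the protocol says the rate is unknown.

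7. **How long.** The last Part 3 patient was randomized between 8 June 2018 (first visit) and 11 July 2018 (first treatment). Section 4.3 closes follow-up at five years from randomization, so between 8 June and 11 July 2023. Amendment 7 is dated 27 January 2023, which leaves 132 to 165 days in the study, before any post-trial access.

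**The case against.** The best defence is that the text is not ambiguous. The parent section, the table and the subject of the paragraph all point to dabrafenib and trametinib, so inserting those two names would be a minor clarification. The protocol reports HLH only with that pair and never classes it as an immune-related event of PDR001. A site that suspects PDR001 has Section 6.3.1 and perhaps Table 6-18. After the final PFS analysis, Sections 6.1.5 and 6.5.3 leave continuation of PDR001 to individual medical judgement, so no visible text forces an investigator to keep giving it.

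Much of this stands, and it rules out a stronger reading. A reader might infer that the protocol contradicts itself evenly, with Section 6.1 and the glossary ordering all three drugs stopped and 6.3.5 ordering PDR001 continued. The documents do not support that. Those definitions are of study treatment, while 6.3.5.9 says only treatment, and usage within 6.3.5 is narrower. Nor does the general remark in 6.3 that "Severe grade or persistent lower grade irAEs typically require interrupting or permanently discontinuing treatment and administration of systemic steroids" settle the matter: it is background, and HLH is not among the reactions listed there.

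The defence does not remove the problem, however. If the local reading is right, the printed rule is to continue PDR001 through suspected and confirmed HLH. That is the less cautious reading for the patient, it departs from the Table 6-18 default for Grade 4 events, and it carries no justification. Room for judgement does not replace an instruction that Amendment 7 added for exactly this hazard.

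**Conclusion.** The point holds as a patient-safety defect that should be fixed. Section 6.3.5.9 omits the drug names, and the surrounding text most naturally fills the gap by keeping PDR001 going. This sits badly with the protocol's own description of HLH and with the default in Table 6-18.

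Few if any patients would be affected: at most 91 on treatment at Amendment 7, not all of them on PDR001, over the limited study time left. The weight comes from the severity of the event. There is no effect on the efficacy analyses.

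The conclusion rests on two conditions. First, a Grade 4 HLH event is taken to fall within the scope of Table 6-18; if it does not, the conflict with that table drops away, but the conflict with the description in 6.3.5.9 remains. Second, Sections 8.1.3 and 8.5 and the PDR001 Investigator's Brochure were not available for this check, so any HLH guidance there is not assessed.

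**What to change.** - In 6.3.5.9, name the drugs in both sentences: PDR001, dabrafenib and trametinib are all interrupted when HLH is suspected and all permanently discontinued when it is confirmed.
- In Table 6-8, add an X for PDR001 in the HLH row.
- In 6.3.5, except 6.3.5.9 from the line that continues PDR001 or placebo, and correct the misspelled drug code.
- If the sponsor does mean PDR001 to continue, say so explicitly in 6.3.5.9 and give the reason.

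The cost is a reworded instruction, one table cell, one exception phrase and a notice to investigators. No data collection, analysis or sample size changes. The clinical downside is that a patient whose HLH is due only to dabrafenib and trametinib would also lose PDR001.

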6.3.6 Follow-up for toxicities

6.3.6.1 Follow up on potential immune related adverse events

The emergence of irAE may be anticipated based on the mechanism of action of immunomodulatory therapies.

Serologic, histologic (tumor sample) and immunological assessments should be performed as deemed appropriate by the Investigator to verify the immune-related nature of the AE and to exclude alternative explanations. Recommendations (Section 6.3) have been developed to assist investigators in assessing and managing the most frequently occurring irAEs.

Subjects whose treatment is interrupted or permanently discontinued due to an irAE, AE or clinically significant laboratory value, must be followed-up at least once a week (or more frequently if required by institutional practices, or if clinically indicated) for 30 days, and subsequently at approximately 30-day intervals (or more frequently if required by institutional practices, or if clinically indicated), until resolution or stabilization of the event, whichever comes first. Appropriate clinical experts should be consulted as deemed necessary.

If an AE is suspected to be immune-related the relevant immunological assessments (e.g., rheumatoid factor, anti-DNA Ab, etc.) should be performed. If cytokine release syndrome is suspected, the assessments outlined in Section 7.2.2.6.8 must be performed. All subjects must be followed-up for irAEs, AEs and SAEs for 150 days following the last dose of PDR001/placebo. However, if the subject begins post treatment antineoplastic medication before the 150-Day safety visit the collection of new SAEs and AEs unrelated to study medication will stop and thereafter only suspected SAEs and suspected AEs will continue to be collected to Day 150. If SAEs suspected to be related to study medication occur beyond Day 150, information should also be collected.

6.3.6.2 Follow up on potential drug-induced liver injury (DILI) cases

[figure not shown]
Subjects with transaminase increase combined with an elevation of total bilirubin (TBIL) may be indicative of potential DILI; these events should be considered as clinically important.

The threshold for potential DILI may depend on the subject's baseline AST/ALT and TBIL value; subjects meeting any of the following criteria will require further follow-up as outlined below:

- For subjects with normal ALT and AST and TBIL value at baseline: AST or ALT > 3.0 x ULN combined with TBIL > 2.0 x ULN
- For subjects with elevated AST or ALT or TBIL value at baseline: [AST or ALT > 2 x baseline AND > 3.0 x ULN] OR [AST or ALT > 8.0 x ULN], combined with [TBIL > 2 x baseline AND > 2.0 x ULN]

Medical review needs to ensure that liver test elevations are not caused by cholestasis, defined as ALP elevation > 2.0 x ULN with R value < 2 in subjects without bone metastasis, or elevation of ALP liver fraction in subjects with bone metastasis.

Note: (The R value is calculated by dividing the ALT by the ALP, using multiples of the ULN for both values. It denotes whether the relative pattern of ALT and/or ALP elevation is due to cholestatic ($R \leq 2$), hepatocellular ($R \geq 5$), or mixed ($R > 2$ and < 5) liver injury).

In the absence of cholestasis, these subjects should be immediately discontinued from study drug treatment, and repeat LFT testing as soon as possible, preferably within 48 hours from the awareness of the abnormal results. The evaluation should include laboratory tests, detailed history, physical assessment and the possibility of liver metastasis or new liver lesions, obstructions/compressions, etc.

1. Laboratory tests should include ALT, AST, albumin, creatine kinase, total bilirubin, direct and indirect bilirubin, GGT, prothrombin time (PT)/INR and alkaline phosphatase.
2. A detailed history, including relevant information, such as review of ethanol, concomitant medications, herbal remedies, supplement consumption, history of any pre-existing liver conditions or risk factors, should be collected.
3. Further testing for acute hepatitis A, B, C or E infection and liver imaging (e.g., biliary tract) may be warranted.
4. Additional testing for other hepatotropic viral infection (e.g., CMV, EBV, Adenovirus, HSV, HHV6, HIV), autoimmune hepatitis or liver biopsy may be considered as clinically indicated or after consultation with specialist/hepatologist.

All cases confirmed on repeat testing meeting the laboratory criteria defined above, with no other alternative cause for LFT abnormalities identified should be considered as “medically significant”, thus, met the definition of SAE ([Section 8.2.1](#)) and reported as SAE using the term “potential drug-induced liver injury”. All events should be followed up with the outcome clearly documented.

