	
(Infliximab is contraindicated in subjects with sepsis or a perforation). Upon symptomatic relief initiate a prolonged steroid taper over 45 to 60 days.
 
 If symptoms worsen during steroid reduction, initiate a re-tapering of steroids starting at a higher dose followed by a more prolonged taper and administer infliximab. If symptoms persist despite the above treatment, a surgical consult should be obtained. 	
 Permanently discontinue dabrafenib and trametinib.
Grade 4: Life-threatening consequences; urgent intervention indicated	
 Same as Grade 3 	
 Permanently discontinue PDR001/placebo, dabrafenib and trametinib.

6.3.3.2 Mandatory dose modifications and recommended clinical management guidelines for abnormal liver enzyme test

Guidelines for dose modification and management of abnormal liver enzyme functions considered to be related to study treatment by the investigator are provided in [Table 6-10](#).

In addition to the instructions below, subjects with normal baseline transaminases and bilirubin who experience sudden elevations even within Grade 1, should be monitored more closely.

Table 6-10 Mandatory dose modifications and recommended clinical management guidelines for abnormal liver enzyme test

Abnormal liver enzyme tests/hepatitis		
Grade	Recommended adverse event management guidelines	Mandatory dose modification requirements
Grade 2: AST or ALT >3× ULN to ≤ 5× ULN and/or bilirubin > 1.5× ULN to ≤ 3× ULN	
 Monitor hepatic laboratory tests more frequently (every 2-3 days) until returned to baseline values 	
 Interrupt PDR001/placebo, dabrafenib and trametinib until ≤ Grade 1, and then reinstate PDR001/placebo, dabrafenib and trametinib at the same dose level.

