Grade 3 or 4: AST or ALT > 5× ULN and/or bilirubin > 3× ULN	
 Monitor hepatic laboratory tests more frequently (every 2-3 days) until return to baseline values. Consider appropriate consultation* with hepatologist and liver biopsy to establish etiology of hepatic injury, if necessary If after 2-3 days new liver assessment shows worsening of laboratory test consider to initiate treatment with high dose steroids (1 to 2 mg/kg/day prednisone or equivalents) 	
 Permanently discontinue PDR001/placebo only if causality is suspected to be related to PDR001/placebo ** If lab results show worsening, follow the management and dose modification (instructions below) 
1st occurrence
 
 Interrupt dabrafenib and trametinib until recovery to ≤ Grade 1 or baseline 
 Reduce dabrafenib and trametinib to the next lower dose level per Table 6-7. Re-escalation of the subject's

Abnormal liver enzyme tests/hepatitis

Grade	Recommended adverse event management guidelines	Mandatory dose modification requirements
	
 Add prophylactic antibiotics for opportunistic infections Start steroid taper as outlined in Section 6.3.4.1 if symptoms improve to Grade ≤ 1 If serum transaminase levels do not decrease 48 hours after initiation of systemic steroids, oral mycophenolate mofetil 500 mg every 12 hours may be given. Infliximab is not recommended due to its potential for hepatotoxicity 	
dose is recommended if criteria in Section 6.3.2 are met.
 
 If no recovery to \leq Grade 2 within 10 weeks, permanently discontinue dabrafenib and trametinib. 
2nd occurrence
 
 Interrupt dabrafenib and trametinib until \leq Grade 1. Reduce dabrafenib and trametinib to the next lower dose level per Table 6-7. Re-escalation of the subject's dose is recommended if criteria in Section 6.3.2 are met. 
3rd occurrence
 
 Permanently discontinue dabrafenib and trametinib

*Rule out viral hepatitis and other potential causes of liver injury

**For patients with liver metastasis who begin treatment with Grade 2 AST or ALT, if AST or ALT increase by $\geq 50\%$ relative to baseline and last for at least 1 week then the patient should be discontinued

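### In 6.3.6.2 the bone-metastasis limb of the cholestasis definition has no R condition, so a hepatocellular case (R ≥ 5) with any rise in liver-fraction ALP falls outside the immediate study-drug stop

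*Protocol*

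**What the plan says.** Protocol 6.3.6.2 first sets the laboratory trigger for a potential DILI case. With normal baseline values it is AST or ALT above 3.0 x ULN together with total bilirubin (TBIL) above 2.0 x ULN. A review step follows: "Medical review needs to ensure that liver test elevations are not caused by cholestasis". Cholestasis is then defined in two limbs:

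- **No bone metastasis:** ALP above 2.0 x ULN and R below 2.
- **Bone metastasis:** "or elevation of ALP liver fraction in subjects with bone metastasis". No R value and no multiple of ULN is attached.

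The Note below explains R: "The R value is calculated by dividing the ALT by the ALP, using multiples of the ULN for both values". It labels R ≥ 5 hepatocellular, R ≤ 2 cholestatic and values between them mixed, for all subjects.

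The action depends on the definition: "In the absence of cholestasis, these subjects should be immediately discontinued from study drug treatment, and repeat LFT testing as soon as possible". The section ends by reserving the DILI term for serious adverse event (SAE) reporting to confirmed cases for which no alternative cause is found.

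A separate rule stands in 6.3.3.2, Table 6-10. Its scope is "Guidelines for dose modification and management of abnormal liver enzyme functions considered to be related to study treatment by the investigator". For Grade 3 or 4 (AST or ALT above 5 x ULN, or bilirubin above 3 x ULN) it says "Interrupt dabrafenib and trametinib until recovery to ≤ Grade 1 or baseline" and "Monitor hepatic laboratory tests more frequently (every 2-3 days) until return to baseline values". PDR001/placebo is stopped only if it is the suspected cause.

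**The concern.** The two limbs treat the same liver pattern differently. Without bone metastasis, the R condition keeps a hepatocellular injury inside the stopping rule. With bone metastasis, any rise in the liver fraction of ALP meets the definition of cholestasis, however high ALT is in relation to ALP. The Note would call such a case hepatocellular, while the definition a few lines above it says cholestasis.

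Raised transaminases and bilirubin with a hepatocellular pattern are what a DILI rule is meant to catch. The subject at stake is one with bone metastasis and such a pattern, for whom the immediate stop of all study drugs, which requires no causality judgement, does not apply as written.

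**Working it through.** The plan states no figure to reproduce. The check applies the written rule to example laboratory values, which are assumed.

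**Inputs (6.3.6.2 and Table 6-10).** All values are in multiples of ULN, with normal baseline.
- Trigger: ALT > 3 and TBIL > 2 (the AST route is taken up under the objection).
- R = ALT / ALP.
- Cholestasis without bone metastasis: ALP > 2 and R < 2.
- Cholestasis with bone metastasis: liver-fraction ALP elevated.
- Immediate stop: trigger met and no cholestasis.
- Table 6-10 Grade 3-4: AST or ALT > 5, or bilirubin > 3.

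**Step 1. Apply the rule.** Total and liver-fraction ALP are taken as the same multiple, and the liver fraction counts as elevated when ALP > 1. The last column applies the amendment proposed below (R < 5 required in the bone-metastasis limb).

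| ALT | ALP | TBIL | R | No bone metastasis | Bone metastasis, as written | Bone metastasis, amended |
|---|---|---|---|---|---|---|
| 6 | 1.1 | 2.5 | 5.45 | stop | no stop | stop |
| 8 | 1.5 | 3 | 5.33 | stop | no stop | stop |
| 12 | 2.2 | 3 | 5.45 | stop | no stop | stop |
| 20 | 2.5 | 4 | 8.00 | stop | no stop | stop |
| 7 | 2.0 | 3 | 3.50 (mixed) | stop | no stop | no stop |
| 4 | 3 | 2.5 | 1.33 (cholestatic) | no stop | no stop | no stop |

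The four R ≥ 5 profiles change class on bone metastasis alone. A more extreme case is ALT 12 with ALP 1.1: R = 12 / 1.1 = 10.9.

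**Step 2. Range of affected values.** R ≥ 5 means ALP ≤ ALT / 5. With ALP also above 1.0:
- ALT 5: 5 / 5 = 1.0, so no affected values
- ALT 8: ALP up to 1.6
- ALT 12: ALP up to 2.4
- ALT 20: ALP up to 4.0

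**Step 3. Which row of Table 6-10 applies.** If the ALP in R is above 1.0, R ≥ 5 forces ALT > 5, so the Grade 3-4 row covers every such case that is considered treatment-related. One exception is possible if R uses total ALP. The liver fraction could be raised against its own limit while total ALP is not above ULN. For example, ALT 4.5 and total ALP 0.9 give R = 5.0. With bilirubin no higher than 3 the Grade 2 row then applies, which interrupts all three drugs and resumes them at the same dose.

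**Step 4. Effect of bone ALP on R.** A bone contribution raises total ALP, the denominator, and so lowers R. Bone disease can therefore make a hepatocellular case look mixed or cholestatic, but cannot push R up to 5. It explains why an R < 2 condition on total ALP would not suit this limb. It does not explain accepting R ≥ 5 as cholestasis.

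**The case against.** Four arguments can be made for the text as it stands.

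**Medical review decides causation.** The reviewer asks whether cholestasis caused the elevations and has the Note at hand, which labels R ≥ 5 hepatocellular for everyone. A sensible reviewer would not blame a 10% rise in ALP for a 12-fold ALT. This stands as mitigation, but not as a cure: cholestasis is defined in the same sentence, and to reach the right answer the reviewer must set that definition aside.

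**Leaving R out may be deliberate.** Bone ALP distorts R. This justifies a separate limb, but by step 4 not the inclusion of R ≥ 5.

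**Table 6-10 already acts.** A reader might infer that these subjects simply stay on all drugs. The documents do not support that. For events considered related, dabrafenib and trametinib are interrupted, liver tests are recommended every 2-3 days, and PDR001/placebo is stopped if suspected. In Part 1, ALT above 8 x ULN with normal baseline transaminases was also a dose-limiting toxicity with no cholestasis exception, but that does not extend to Part 3. What remains is a difference in kind. Table 6-10 depends on a causality judgement, and at the first and second occurrence it allows restart at the next lower dose.

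**The lost stop may not be permanent.** Permanence comes from the glossary entry for study treatment discontinuation, "Point/time when patient permanently stops taking study treatment for any reason". Section 6.3.6.2 uses a slightly different phrase, and Table 6-10 says so outright where it means permanent. The permanent reading is reasonable but not certain.

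Two limits also stand. Mixed patterns are not part of the point, because their class depends on which ALP enters R and the protocol defines no liver-fraction R. AST-led cases are not addressed by R at all: AST 10, ALT 2 and ALP 1.1 give R = 2 / 1.1 = 1.8.

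**Conclusion.** The point holds as a minor defect in a safety rule. As written, a subject with bone metastasis, R ≥ 5 and any rise in liver-fraction ALP is defined as cholestatic and falls outside an immediate stop that the same values would trigger without bone metastasis. The loss is the causality-independent discontinuation of all study drugs, whose permanence rests on the glossary. The DILI term for SAE reporting may also be lost, if the cholestasis class is taken as an alternative cause.

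A reader might go further and infer that the whole DILI work-up or all SAE reporting falls away. The text does not clearly say so: the cholestasis condition stands in the sentence on stopping and repeat testing, and whether it also governs the evaluation is open.

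The protocol text at hand gives neither a bone-metastasis rate nor a rate of DILI triggers, so the number of subjects cannot be estimated. It is probably small. No endpoint, error rate or sample size is affected. The example values assume normal baseline and ALT as the trigger.

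**What to change.** Keep the limb "or elevation of ALP liver fraction in subjects with bone metastasis" and add: provided that R, calculated as in the Note, is below 5; a case with R of 5 or more is not to be classed as cholestasis.

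Because bone ALP can only lower R from total ALP, this wording cannot label a case hepatocellular on account of bone disease. It needs no new laboratory definition, and it leaves mixed patterns and AST-led cases to medical review as now. It does not catch every case: with ALT 12, liver ALP 1.1 and total ALP raised by bone disease to 3 x ULN, R is 12 / 3 = 4.0 and the limb still applies. Requiring R < 2 on the liver fraction would reach further. But it needs a liver-fraction R and reference limit that the protocol does not define, would bring in mixed patterns, and would stop treatment in some subjects with true mild cholestasis.

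The cost is one sentence in 6.3.6.2, and a few more DILI stops and SAE reports in subjects with bone metastasis.
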